#### 2.6. Rationale for Baseline Dose Selection

[figure not shown]
Among 51 AML patients on crenolanib monotherapy, 28 patients have received 100 mg TID and the rest at higher dose of 66 mg/m² TID. Most common adverse events were nausea, vomiting and diarrhea and LFT elevations. As crenolanib will be given in combination with standard salvage chemotherapy or with 5-Azacytidine, a dose escalation schedule will be utilized for this trial. The starting dose of crenolanib at 60 mg TID is 40% less than the dose (100 mg TID) that has been found to be well tolerated in previous phase II studies. If the 60 mg TID is proved to be safe and tolerable in the combination regimen, dose escalations to 80 mg TID and 100 mg TID will be studied. Representative plasma inhibitory activity (PIA) assay from single-agent crenolanib studies showed this dose schedule effectively inhibited the phosphorylated FLT3 (Figure 2.6).

Figure 2.6 Representative PIA result of AML patient samples after single dose crenolanib

To date, 28 AML patients have been treated with 100 mg TID crenolanib. Day 1 pharmacokinetics data is shown in Figure 2.7.

Figure 2.7 Serum concentrations of crenolanib following single dose (100 mg) in AML patients

#### 3. STUDY DESIGN

This is a Phase I/II, two arm, open label study in FLT3 mutation positive AML of treatment given as either:

Arm 1: crenolanib with standard salvage chemotherapy

Arm 2: crenolanib with 5-azacitidine

Assignment to treatment arm will be determined by the Investigator with enrollment to each arm to occur simultaneously.

Crenolanib will be administered for the phase 1 portion as described according to dose levels in Table 6.2. Phase I will use a rolling-6 design and plan for a total of 18 patients on each arm. The starting dose will be 60 mg TID (dose level 1). Dose escalations will proceed to 80 mg TID (dose level 2) and 100 mg TID (dose level 3) based on DLTs (as defined in section 6.3). DLTs will be evaluated during the first cycle of crenolanib treatment. Patients who experience crenolanib related DLTs at dose level 1 will receive a dose reduction to dose level 0 (60 mg BID). Patients who encounter DLTs at dose levels 2 and 3 will receive dose reduction at 1 dose level lower.

Phase II total of 26 patients in each arm treated at established phase I dose.

#### 4. PATIENT SELECTION

Patients must have baseline evaluations performed within 28 days prior to enrollment (unless otherwise specified in the schedule of events) and must meet all inclusion and exclusion criteria. Results of all baseline evaluations must be reviewed by the Principal Investigator or his/her designee prior to enrollment of that patient. In addition, the patient must be thoroughly informed about all aspects of the study, including the study visit schedule and required evaluations and all regulatory requirements for informed consent. The written informed consent must be obtained from the patient prior to initiating treatment. The following criteria apply to all patients enrolled onto the study unless otherwise specified.

#### 4.1. Inclusion Criteria

- 1. Confirmed diagnosis of refractory/relapsed AML or high-risk MDS (IPSS intermediate-2 risk and high risk, see Appendix VIII) that is refractory or has relapsed after prior therapy. Patients with secondary leukemia (i.e., evolving from MDS or MPN, or secondary to therapy for other malignancies) are eligible
  - Arm 1: Subjects must have received at least one prior therapy and a maximum of three prior therapies
  - Arm 2: Subjects must have received at least one prior therapy and a maximum of three prior therapies. No prior treatment with 5-Azacitidine is allowed in this arm.
- 2. Presence of FLT3 ITD and/or other FLT3 activating mutations
- 3. Extramedullary disease is allowed except for active CNS disease
- 4. Prior use of hydroxyurea or isolated doses of cytarabine for palliation (i.e., control of WBC) are allowed but should be discontinued at least 24 hrs prior to study start. Other agents used strictly

with palliative intent might be allowed during this period after discussing with principal investigator

- 5. Age ≥18 years
- 6. ECOG PS 0-2
- 7. Adequate liver function tests will be required within 72 hours of enrollment. Adequate liver function will be defined as:
  - Normal total serum bilirubin
  - ALT and AST  $\leq 2.0 \text{ x ULN}$
- 8. Adequate renal function, defined as serum creatinine  $\leq 1.5 x$  ULN
- 9. Negative pregnancy test, within 72 hours of enrollment, for women of childbearing potential "Woman of childbearing potential" is defined as any woman who has not undergone a hysterectomy and who has had menses at any time in the preceding 24 consecutive months
- 10. Able and willing to provide written informed consent

#### 4.2. Exclusion Criteria

- 1. Absence of FLT-3 activating mutations at time of study screening
- 2. < 5% blasts in blood or marrow at screening, except if measurable extramedullary AML is confirmed
- 3. Subjects with Acute promyelocytic leukemia (APL)
- 4. Known clinically active CNS leukemia
- 5. Clinically active or unstable graft-versus-host disease requiring treatment which precludes administration of chemotherapy as defined in this protocol
- 6. Therapy with curative intent for relapsed AML or high-risk MDS prior to the first dose of crenolanib as follows: within 14 days of study enrollment for classical cytotoxic agents and for 5x the half-life for FLT3 targeting TKI, hypomethylating agents or MEK inhibitors
- 7. Patient with pre-existing liver diseases (i.e. cirrhosis, chronic hepatitis B or C, nonalcoholic steatohepatitis, sclerosing cholangitis)
- 8. Patients with known HIV infection
- 9. "Currently active" second malignancy (other than non-melanoma skin cancer, carcinoma in situ of the cervix or prostatic intraepithelial neoplasia within 1 year). Subjects are not considered to have a "currently active" malignancy if they have completed therapy and are considered by their physician to be at less than 30% risk of relapse within 1 year
- 10. Subject with concurrent severe and/or uncontrolled medical conditions that in the opinion of the investigator may impair the participation in the study or the evaluation of safety and/or efficacy.
- 11. Subject with uncontrolled cardiac disease including congestive heart failure class III or IV by the NYHA, unstable angina (anginal symptoms at rest) or new onset angina (began within the last 3 months) or myocardial infarction within the past 6 months
- 12. Pregnant or breastfeeding women
- 13. Inability to give an informed consent

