#### **Exclusion Criteria**

- 1. Absence of FLT-3 activating mutations at time of study screening
- 2. < 5% blasts in blood or marrow at screening, except if measurable extramedullary AML is confirmed
- 3. Subjects with Acute promyelocytic leukemia (APL)
- 4. Known clinically active CNS leukemia
- 5. Clinically active or unstable graft-versus-host disease requiring treatment which precludes administration of chemotherapy as defined in this protocol
- 6. Therapy with curative intent for relapsed AML or high-risk MDS prior to the first dose of crenolanib as follows: within 14 days of study enrollment for classical cytotoxic agents and for 5x the half-life for FLT3 targeting TKI, hypomethylating agents or MEK inhibitors
- 7. Patient with pre-existing liver diseases (i.e. cirrhosis, chronic hepatitis B or C, nonalcoholic steatohepatitis, sclerosing cholangitis)
- 8. Patients with known HIV infection
- 9. "Currently active" second malignancy (other than non-melanoma skin cancer, carcinoma in situ of the cervix or prostatic intraepithelial neoplasia within 1 year). Subjects are not considered to have a "currently active" malignancy if they have completed therapy and are considered by their physician to be at less than 30% risk of relapse within 1 year
- 10. Subject with concurrent severe and/or uncontrolled medical conditions that in the opinion of the investigator may impair the participation in the study or the evaluation of safety and/or efficacy.

	11 Cubiast with uncontrolled and in diameter in 1 P
	
 
11. Subject with uncontrolled cardiac disease including congestive heart failure class III or IV by the NYHA, unstable angina (anginal symptoms at rest) or new onset angina (began within the last 3 months) or myocardial infarction within the past 6 months
 
12. Pregnant or breastfeeding women
 
13. Inability to give an informed consent
 

Treatment	Arm 1:
	Induction (up to 2 cycles)
	Physician's choice standard salvage chemotherapy regimen:
	Ida/Cytarabine Idarubicin 12 mg/m² IV over 1 hr daily on Days 1-3 Cytarabine 1.5 g/m² IV continuously over 3 hr on Days 1-4 (≤ 60 yrs) or Days 1-3 (> 60 yrs) Crenolanib PO starting on Day 5 (+3 day window) continuously
	MEC + crenolanib Mitoxantrone 8 mg/m² IV, push on Days 1-5
	Etoposide 100 mg/m² IV on Days 1-5
	Cytarabine 1000 mg/m² IV, over 3 hours on Days 1-7
	Crenolanib 100 mg TID starting on Day 8 (+3 day window) continuously

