#### 5.3. Study Conduct and Definitions of DLT and MTD

#### **5.3.1. Definition of DLT**

DLT is defined as any clinically significant adverse event or abnormal laboratory value occurring during the first cycle of therapy that is not related to concomitant medications, co-morbidities or underlying disease (leukemia), and that is not expected for the chemotherapy being used together with crenolanib.

- Non-hematologic DLT is defined as any grade 3 or 4 non-hematologic toxicities despite optimal supportive care. For example, grade 3 or 4 nausea, vomiting, or diarrhea that cannot be controlled with standard antiemetic or antidiarrheal medications used at optimal dose within 72 hours of onset are considered DLTs.
  - Tumor lysis syndrome is considered DLT. If 2 out of the 10 first patients are observed to experience the tumor lysis syndrome of Grade 4, the trial will be put on hold and a mitigation strategy will be implemented.
- Hematologic DLT is defined as grade ≥3 neutropenia and/or thrombocytopenia with a hypocellular bone marrow lasting for 6 weeks or more after the last dose of therapy in the absence of residual leukemia (i.e., with less than 5% blasts).
  - o Anemia will not be considered for the definition of DLT.

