10. CRITERIA FOR RESPONSE

For AML, response criteria will be modified from the International Working Group for AML [28]. Responders are patients who obtain a CR, CRi, or PR, with or without cytogenetic response, hematologic improvements, and morphologic leukemia-free state. Briefly, criteria are as follows:

(1).	Complete Remission (CR)
	Peripheral blood counts:
	No circulating blasts
	Neutrophil count $\geq 1.0 \times 10^9 / L$
	Platelet count $\geq 100 \text{ x} 10^9 / \text{L}$
	Bone marrow aspirate and biopsy:
	≤5% blasts
	No Auer rods
	No extramedullary leukemia
(2).	Complete Remission with Incomplete Blood Count Recovery (CRi)
	Peripheral blood counts:
	No circulating blasts
	Neutrophil count $<1.0 \times 10^9/L$ , or
	Platelet count $<100 \text{ x} 10^9/\text{L}$
	Bone marrow aspirate and biopsy:
	≤ 5% blasts
	No Auer rods
	No extramedullary leukemia
(3).	Partial Remission (PR)
	50 % reduction in bone marrow blast and to >5% and <20%.
(4).	Morphologic Leukemia-Free State
	Bone marrow: ≤ 5% myeloblasts
(5).	Hematologic Improvement (HI)
Her	natologic response must be described by the number of positively affected cell lines.
	Erythroid response (E) (pretreatment Hgb <11 g/dL)
	Hgb increase by $\ge 1.5 \text{ g/dL}$
	Platelet response (P) (pretreatment platelets $<100 \text{ x} 10^9/\text{L}$ )
	Absolute increase of $\ge 30 \times 10^9 / L$ for patients starting with $> 20 \times 10^9 / L$ platelets
	Increase from $\leq 20 \times 10^9/L$ to $\geq 20 \times 10^9/L$ and by at least $100\%$
	Neutrophil response (N) (pretreatment ANC <1.0 x10  /L)
	At least 100% increase and an absolute increase $> 0.5 \times 10^9/L$
	Blast response (B)
	At least a 50% reduction in blast percentage in peripheral blood (if > 5%) or bone marrow
	For high-risk MDS, response will use the International Working Group criteria [29].

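### In AML, exactly 5% marrow blasts is eligible disease at entry yet within the CR/CRi marrow limit, so a patient can count as a responder with no change or with less than the fall PR requires

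*Combined protocol and SAP*

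**What the plan says.** Exclusion 2 in Section 4.2, repeated in the synopsis, removes patients with "< 5% blasts in blood or marrow at screening, except if measurable extramedullary AML is confirmed". A count of exactly 5% is not below 5%, so it does not exclude.

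Section 10 defines AML response. CR and CRi share a marrow limit of 5% or less. Both also require "No circulating blasts", no Auer rods and "No extramedullary leukemia". They differ in the neutrophil and platelet counts. Neither refers to baseline. PR does, and it starts above 5%: "50 % reduction in bone marrow blast and to >5% and <20" percent. Morphologic leukemia-free state lists one condition, "Bone marrow: ≤ 5% myeloblasts".

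Section 5.3.1 uses a strict limit. Hematologic DLT is judged "in the absence of residual leukemia (i.e., with less than 5% blasts". Section 6.2 uses above 5% marrow blasts, or persistent blood blasts, as the point at which treatment may continue regardless of counts.

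Section 12.1 makes the phase II primary endpoint CR+CRi+CRp+PR after one or two cycles. Section 12.4 lists CR+CRi+PR.

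**The concern.** The primary endpoint should separate patients whose leukemia responded from those whose leukemia did not. At exactly 5% the plan does not do this cleanly. The same marrow value is eligible disease at entry, residual leukemia in the DLT definition, and within the remission limit for the endpoint. CR and CRi describe a state and not a change, so nothing in Section 10 stops a patient who already meets them at screening from being counted later.

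The trial has no concurrent control for response. Each arm is set against a historical 10% with 32 evaluable patients, and few responses separate success from failure. One or two misclassified patients could matter.

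**Working it through.** **1. The cuts side by side (AML)**

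| Place | Rule | Exactly 5% in marrow is |
|---|---|---|
| Section 4.2, exclusion 2 | below 5% excluded | eligible (if both blood and marrow must be below 5% to exclude) |
| Section 5.3.1 | below 5% = no residual leukemia | residual leukemia |
| Section 6.2 | above 5% = continuing disease | not above the limit |
| Section 10, CR and CRi | 5% or less | within the remission limit |
| Section 10, PR | above 5%, below 20%, with 50% fall | outside PR |

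**2. Who is affected**

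- *Enters at exactly 5% and is unchanged.* With no circulating blasts, Auer rods or extramedullary leukemia, this patient meets CR if counts are adequate and CRi if they are not. The fall is 0%.
- *Enters above 5% but below 10% and ends at exactly 5%.* The fall is (b − 5)/b for baseline b. For b = 6 it is 16.7% and for b = 8 it is 37.5%, both short of 50%. The patient counts as CR or CRi if the other conditions are met.
- *Enters at 10% or more and ends at exactly 5%.* For b = 10 the fall is 50%. If 5% were moved into the PR range, this patient would be PR and still a responder. Only the split between CR/CRi and PR changes.

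**3. The plan's own figure**

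Inputs from Section 12.1: n = 32, null rate 0.10, target 0.25, two-sided 10% chi-square test.

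Power = Φ[(0.25 − 0.10 − 1.645·√(0.10·0.90/32)) / √(0.25·0.75/32)] = Φ[(0.15 − 0.0872)/0.0765] = Φ(0.82) = 79.4%.

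This reproduces the stated 79%. The blast cut does not enter it.

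**4. The deciding count**

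Critical count = 32·0.10 + 1.645·√(32·0.10·0.90) = 3.2 + 2.79 = 5.99, so 6 or more responses reject. Check: 6/32 gives z = 0.0875/0.0530 = 1.650, just above 1.645. The step that changes the decision is therefore from 5 to 6.

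Binomial, n = 32:
- true rate 0.10: P(X = 5) = 0.2115 − 0.0944 = 11.7%
- true rate 0.25: P(X = 5) = 0.9302 − 0.8470 = 8.3%

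**5. Size if it happens**

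Each patient is 1/32 = 3.1 points. The documents do not give the number of such patients. As an assumption, let k of 32 be credited without change and let the rest respond at 10%. The expected rate is (k + (32 − k)·0.10)/32, and the chance of success is P(Binomial(32 − k, 0.10) ≥ 6 − k).

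| k | Expected rate | P(6 or more) |
|---|---|---|
| 0 | 10.0% | 9.4% |
| 1 | 12.8% | 19.3% |
| 2 | 15.6% | 35.3% |

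**The case against.** The strongest reply is that the overlap is one value and that several conditions must coincide. Most of this stands, and it limits what can be claimed.

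- A reader might infer that every patient at 5% is in CRi on entry. The documents do not support that. CRi also needs no circulating blasts, no Auer rods and no extramedullary leukemia.
- The no-change route depends on how exclusion 2 is read. If a patient is excluded when either blood or marrow is below 5%, everyone without extramedullary disease enters with circulating blasts. Those admitted under the exception have extramedullary AML. On that reading nobody meets CR or CRi unchanged. The post-treatment route and the conflict with Section 5.3.1 remain.
- A reader might infer that any patient left at 5% after treatment inflates the primary endpoint. Those who fell from 10% or more would be PR under a stricter cut and remain responders.
- A reader might count leukemia-free state as a route into the endpoint, because Section 10 says "Responders are patients who obtain a CR, CRi, or PR, with or without cytogenetic response, hematologic improvements, and morphologic leukemia-free state". That sentence is ambiguous, and the endpoint lists in Sections 12.1 and 12.4 do not include it.
- High-risk MDS uses separate cited criteria, so the point concerns AML only.
- Section 4.1 requires confirmed relapsed or refractory disease. The investigator reviews baseline results, and the sponsor confirms eligibility. This narrows the gap but does not close it, since no rule bars a patient at exactly 5%.

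**Conclusion.** The concern holds in a narrow form. The blast cuts in Sections 4.2, 5.3.1, 6.2 and 10 do not agree at exactly 5%. As a result, the CR/CRi rule can credit an AML patient whose marrow has not changed, or has changed by less than PR would require.

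The documents give neither the baseline blast distribution nor the precision to which counts are reported. The share of patients affected is therefore unknown and probably small. One such patient would be enough to about double the false-positive probability (9.4% to 19.3%), but this is a conditional figure and not a forecast. It assumes one credited patient in 32, a true 10% rate in the others, and success at 6 or more under the stated test. The no-change route also rests on reading exclusion 2 as requiring both counts to be below 5%.

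No general inflation of the primary endpoint is shown. This is a minor definitional fault that is easily repaired.

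**What to change.** - Use one non-overlapping cut for eligibility and endpoint classification. For example, in Section 10 set the marrow limit for CR, CRi and leukemia-free state at below 5%, and PR from 5% to below 20% with the 50% fall kept. The PR bound must move with the others, or exactly 5% falls in no category. A marrow count that makes a patient eligible as active disease then cannot also meet the remission limit.
- State in Section 4.2 and the synopsis whether exclusion 2 applies when either, or only when both, of blood and marrow are below 5%.
- Reconcile Section 5.3.1 (below 5%) and Section 6.2 (above 5%) with the chosen cut. Any rule on continuing treatment is for the sponsor to settle.

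The cost is wording, and a response rate that may be slightly lower. The sample size of 32 evaluable patients per arm and the 79% power are unaffected.

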#### 5. TREATMENT PLAN

#### 5.1. General

Patients will be assigned to treatment arm by physician's choice and according to the availability of slots.

The study will enroll patients with relapsed/refractory AML with FLT3 activating mutations. There will be two parallel two arms. In Arm 1 patients will be treated with standard salvage chemotherapy combined with crenolanib. In Arm 2 patients will receive azacitidine combined with crenolanib. Arms 1 and 2 will enroll simultaneously. For both arms, patients will be treated with crenolanib at a starting dose level of 1 (60 mg TID) as defined in the Table 6.2. De-escalation to dose level 0 (60 mg BID) is possible in the event that dose level 1 is found to be too toxic. The dose escalation will proceed independently in each arm. In arm 1 a cycle of induction or consolidation can last for a minimum of 28 days and a maximum of 60 days (extending a cycle for more than 60 days would require a conversation with the sponsor); maintenance cycles will be defined as 28 days. In arm 2 a cycle is defined as 28 days. The first cycle of treatment (in arm 1 and arm 2 independently) will constitute the dose-limiting toxicity (DLT) evaluation period. Study drug will be taken continuously until one of the criteria for study discontinuation is fulfilled.

For each arm of the study, the first 6 patients will be treated at a dose level of 1(60 mg TID). Patients will be entered sequentially to subsequent dose levels, dose level 2 (80 mg TID) and dose level 3 (100 mg TID) after DLTs have been assessed and it is safe to dose escalate. The Rolling-6 design will be used. The Rolling-6 design aims to shorten the duration of Phase I trials by minimizing the time the trial would be closed to accrual for toxicity monitoring. This is achieved by enrolling anywhere from 2 to 6 patients at a dose level without requiring that the DLT status of the patients already assigned to the same dose level are known.

Dose Escalation/De-Escalation Rules in phase I

The following table enumerates all possible scenarios and describes escalation/de-escalation rules that will be applied during dose-finding, separately in each arm:

Table 5.1. Dose escalation/de-escalation rules for the Rolling-6 design

	Dose	e Escalation/De-	Escalation Rules fo	r the Rolling-6 D	Design
				Decision when	n Next Patient is Enrolled
# Pats Enrolled	# Pats with DLTs	# Pats w/o DLT	# Pats with Toxicity Data Pending	Not at the Highest Dose Level	At the Highest Dose Level
2	0, 1	Any	Any	Stay	
2	2	0	0	De-escalate	
3	0	0, 1, 2	3, 2, 1	Stay	
3	0	3	0	Escalate	

3	1	0, 1, 2	2, 1, 0	Stay	
3	$\geq 2$	Any	Any	De-escalate	
4	0	0, 1, 2, 3	4, 3, 2, 1	Stay	Stay
4	0	4	0	Escalate	Stay
4	1	0, 1, 2, 3	3, 2, 1, 0	Stay	Stay
4	≥ 2	Any	Any	De-escalate	De-escalate
5	0	0, 1, 2, 3, 4	5, 4, 3, 2, 1	Stay	Stay
5	0	5	0	Escalate	Stay
5	1	0, 1, 2, 3, 4	4, 3, 2, 1, 0	Stay	Stay
5	$\geq 2$	Any	Any	De-escalate	De-escalate
6	0	0, 1, 2, 3, 4	6, 5, 4, 3, 2	Suspend	Suspend
6	0	5, 6	1, 0	Escalate	MTD not determined
6	1	0, 1, 2, 3, 4	5, 4, 3, 2, 1	Suspend	Suspend
6	1	5	0	Escalate	MTD not determined
6	≥ 2	Any	Any	De-escalate	De-escalate

The MTD is empirically defined as the highest dose level at which 6 patients have been treated with at most 1 patient experiencing a crenolanib related DLT and the next higher dose level has been determined to be too toxic. The maximum tolerated dose (MTD) may be further defined based on incidence of delayed or cumulative toxicity.

Approximately 88 patients (a maximum of 18 patients in each arm for determination of MTD and 26 patients each arm for phase II portion) will be enrolled in the study. In the dose finding phase I, a maximum of 6 patients at each dose level will be enrolled to establish the proper dose for phase II. As a result, as few as 6 patients and as many as 18 patients can be enrolled in phase I. The recommended dose of crenolanib for testing in the expansion phase will be tentatively identified in the dose escalation phase and will be that which is at or below the MTD, that can be delivered safely in multiple cycles with an acceptable incidence of on-time delivery, and that confers exposure consistent with that needed for efficacy based on the nonclinical models. Once the proper dose has been determined for phase II, an additional 26 patients will be enrolled in each arm.

Table 5.2. Dose levels of crenolanib (applies to both Arms 1 and 2)

Dose Level	Crenolanib mg PO daily during induction
0	60 mg BID
1 (Starting dose)	60 mg TID
2	80 mg TID
3	100 mg TID

Dose adjustments beyond those mentioned in this table or different to the doses specified may be acceptable after discussion with the PI and notification of the sponsor and documentation of the justification recorded in the chart.

